We are proposing to conduct a within subject, placebo controlled, cross-over study in which 52 subjects will complete a study in which each subject will receive 12 days of placebo and 12 days of levomilnacipran in random order. During the last five days of taking medication or placebo, subjects will attempt to quit smoking with abstinence confirmed at daily visits. The number of days smokers are successfully abstinent will be compared between levomilnacipran and placebo.

The following specific aim will be pursued:

1) Determine the importance of norepinephrine reuptake inhibition as a mechanism by which a medication can increase smoking cessation rates

We hypothesize that levomilnacipran (relative to placebo) will in a laboratory study alter smoking behavior in a manner consistent with a medication effective at increasing smoking cessation rates.

3 Background

The morbidity and mortality associated with cigarette smoking has been well described.⁷ The best available therapies, however, result in less than a third of smokers remaining abstinent 6 months after cessation.¹ Clearly, it is imperative that strategies are developed to increase smoking cessation rates. There are currently only two non-nicotine medications that are approved in the United States for smoking cessation. Two additional medications are recommended as second line therapies in clinical practice guidelines (i.e., nortriptyline, clonidine), however only one of these agents (i.e., nortriptyline) has consistent data demonstrating its efficacy, with the recommendation to not use it as first line largely due to its high rates of adverse effects rather than questions regarding efficacy (conversely, the data with clonidine is mixed but meta-analyses have found it to be effective).^{1,8} All of the currently available medications therefore have limited efficacy and many have questions regarding their safety (e.g. varenicline has been associated with neuropsychiatric adverse effects; nortriptyline is associated with anticholinergic and antihistaminic side effects and toxicity in overdose). It is critical that new medications are identified to treat tobacco dependence. This is particularly true for smokers of menthol cigarettes (who are predominantly African American) as currently available medications appear to be even less effective in this group.⁹

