c) Subjects: Volunteers for this study will be recruited through flyers, advertisement and word of mouth. This study will be described in recruitment notices as an evaluation of the short-term effects of a medication to help smokers quit but also 'not as a treatment study.' This is consistent with how similar studies assessing medication efficacy have been advertised.⁵ Approximately 19% of the population in Minnesota smokes. There are therefore a sufficient number of smokers in the population to enroll the required number of study subjects. We will be recruiting generally healthy smokers (smoking on average, ≥ 8 cigarettes per day) who are motivated to quit smoking. Motivation to quit will be determined by self-report. Due to potential neuropsychiatric side effects of antidepressants in adolescents and young adults, we will only be recruiting subjects over the age of 24. Smokers with medical or psychiatric conditions likely to place them at increased risk if they were to participate in the study or whose conditions might interfere with data interpretation will be excluded. Similarly, smokers taking medication that might interfere with measures to be studied (e.g. psychiatric medications) or that would be expected to interact with or be unsafe to take with levomilnacipran will be excluded.

Inclusion criteria are as follows:

- 1) Be between ≥ 25 years old and ≤ 55 years old
- 2) Smoke, on average, at least 8 cigarettes per day for a period longer than 1 year
- 3) Indicate motivation to quit smoking

Exclusion criteria are as follows:

- 1) Current serious or unstable medical or psychiatric condition (as determined by self-reported medical history, the PRIME-MD and a physical exam)
- 2) Use of medication that could interfere with measures to be studied (e.g. psychiatric medications) or that would be expected to interact with levomilnacipran (e.g. strong inhibitors of CYP3A4)

- 3) Substance abuse within six months of beginning the study based on self-report
- 4) Regularly use any form of nicotine or tobacco other than cigarettes
- 5) Are pregnant or breast feeding (female subjects will be given a urine pregnancy test at the screening visit with pregnancy later in the study and breast feeding based on self-report)

We are planning to recruit an equal number of menthol and non-menthol cigarette smokers. To qualify as a menthol smoker, greater than 80% of cigarettes smoked are menthol.

c) Procedures

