c.1) Screening visit: Initial eligibility will be assessed via a phone interview. Those likely to qualify will be scheduled for a screening visit at which written informed consent will be obtained and eligibility confirmed. Psychiatric exclusion will be based on the Primary Care Evaluation of Mental Disorders (PRIME-MD) instrument. The PRIME-MD, designed to be administered by non mental health professionals, has been found to have good agreement with assessments made independently by mental health professionals.¹³ Medical history will be obtained via subject report and a physical exam will be performed to ensure that subjects are in generally good health. A urine pregnancy test will be given to females to confirm that they are not pregnant. Following the screening visit, those subjects who qualify will be scheduled for the remainder of their visits.

c.2) Experimental Protocol: Subjects will participate in two evaluation periods each lasting three weeks. During one of the evaluation periods levomilnacipran will be evaluated whereas during the other evaluation period, placebo will be evaluated. Procedures for the two evaluation periods will be identical, with the order of which period occurs first (i.e. medication or placebo) assigned randomly. The procedures at each study visit are based on published methods. The first week of each period will consist of baseline smoking assessment. This week will also serve as a medication washout period when occurring as the first week of the second three week assessment period (with a terminal half-life of approximately 12 hours,¹¹ this should be a sufficiently long washout period). During this week subjects will be seen at the research clinic twice. At the second baseline week visit subjects will receive their initial supply of medication. Levomilnacipran will be dosed at 20 mg once daily for two days followed by 40 mg once daily for 10 days. This is consistent with the recommended dose for the treatment of depression.

During the second week of the evaluation period, subjects will begin to take their assigned medication (i.e. levomilnacipran or placebo) and will be seen at two visits. At the first of these visits, subjects will receive a supply of the 40 mg dose of medication (or placebo). Adverse events and subjective measures such as craving and withdrawal symptom severity will be assessed at each visit.

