During the third week of the evaluation period, subjects will attempt to abstain from smoking for a five day period and will be seen daily to determine smoking status. These visits will occur on five consecutive days with the visits in most instances occurring Monday through Friday. Subjects will be told to smoke normally until the evening prior to the first of the abstinence assessment days and then to attempt to not smoke at all during the subsequent five days. At each visit, smoking status will be evaluated by measuring exhaled carbon monoxide (CO) concentrations with a value of < 5 ppm confirming abstinence. Each visit during this week will be scheduled in the afternoon in order to assess mid-day CO rather than CO after just waking up. Subject will stop taking medication after they complete their five consecutive days of study visits.

The same procedures will then be repeated except that subjects will receive the alternate treatment. Since continued participation in the study will require subjects to resume smoking, subjects will be told that it is not necessary for them to resume smoking if they wish to remain abstinent; however they would not be able to continue participation in the study if this were the case. At the conclusion of the study, subjects will be given information about resources in the community that could assist them with the smoking cessation attempt. They will additionally be called by telephone approximately 1 week after completing the study in order to ensure that there are no adverse events and to ascertain if they have attempted to quit smoking. Those that have not made a cessation attempt will be encouraged to do so and will again be provided with information regarding community resources to assist them.

Subjects will therefore be seen at a screening visit and at 9 visits per study period for a total of 19 visits.

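### Optional, low-cost safety improvement: the only pregnancy test is at screening, so a placebo-first woman starts levomilnacipran nominally about 28 days or more after it

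*Combined protocol and SAP*

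**What the plan says.** Exclusion criterion 5 (section 4, Subjects) bars pregnant and breast-feeding women and sets out how this is checked: "female subjects will be given a urine pregnancy test at the screening visit with pregnancy later in the study and breast feeding based on self-report". Section c.1) Screening visit agrees: "A urine pregnancy test will be given to females to confirm that they are not pregnant". It then continues: "Following the screening visit, those subjects who qualify will be scheduled for the remainder of their visits". No time limit between screening and period 1 is stated, and none of the visits described in c.2) includes another pregnancy test.

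On dosing, section 2 states that "each subject will receive 12 days of placebo and 12 days of levomilnacipran in random order". Section c.2) says of each three-week period: "At the second baseline week visit subjects will receive their initial supply of medication". Dosing begins in the second week and ends after the five daily quit-week visits. The first week of period 2 doubles as the washout. Section c.2) also says: "Procedures for the two evaluation periods will be identical".

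Section 7 (DSMP) has subjects asked about side effects at every visit. Its reasons for discontinuation include a significant new medical condition but do not name pregnancy.

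**The concern.** A pregnancy test protects against exposure only for a limited time after it is done. Here it is fixed to screening, while the crossover delays active drug by three further weeks in half the subjects. For placebo-first women the only objective check is therefore about four weeks old, or older, when the first active dose is taken. Self-report and the side-effect question can bring out a pregnancy that the woman knows about or that causes symptoms. They cannot bring out one she has not recognised.

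What is at stake is exposure that the plan's own exclusion is meant to prevent: up to 12 days of levomilnacipran at 20 to 40 mg in a woman who satisfied every written check.

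**Working it through.** The documents state no test-to-dose interval, so it has to be derived from the schedule.

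**Reproducing the plan's own figures**
- Visits: 1 screening + 2 × (2 baseline + 2 titration + 5 quit-week) = 19, matching section c.2).
- Dosing days per period: 2 at 20 mg + 10 at 40 mg = 12, matching section 2.

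**Day of first dose** (day 1 = Monday of week 1 of period 1)
- The quit week is usually Monday to Friday of week 3, which is days 15 to 19 of a period.
- A 12-day course ending on day 19 starts on day 19 − 12 + 1 = 8.
- Period 2 adds 21 days, since the washout lies inside its first week.

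| | First levomilnacipran | Days after day 1 | Last levomilnacipran | Days after day 1 |
|---|---|---|---|---|
| Drug first | day 8 | 7 | day 19 | 18 |
| Placebo first | day 21 + 8 = 29 | 28 | day 21 + 19 = 40 | 39 |

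**Adding the unstated screening gap** (assumed values), placebo first: 0 days gives 28; 7 days gives 35; 14 days gives 42. Drug first: 7, 14 and 21.

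**Other checks before active drug.** A placebo-first woman attends 9 + 2 = 11 period visits before her first active dose. The side-effect question is asked at each, and none includes a pregnancy test.

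**How many women** (assumptions, not in the documents: 40% to 60% women, split evenly by sequence; 50% to 90% of them of childbearing potential)
- Placebo-first women among the 52 planned completers: 52 × 0.40 / 2 = 10.4 to 52 × 0.60 / 2 = 15.6.
- Of childbearing potential: 10.4 × 0.50 = 5.2 to 15.6 × 0.90 = 14.0.
- Illustration, with 0.1% to 1% having an unrecognised conception in 28 days: 5.2 × 0.001 = 0.005 to 14.0 × 0.01 = 0.14 expected in the whole trial.

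Completers are the right base. The plan expects 20% attrition from the 64 enrolled, and of subjects who choose to stay abstinent after period 1 it says "however they would not be able to continue participation in the study if this were the case".

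**With a retest at the second baseline-week visit.** The day of that visit is not stated; days 2 to 7 are assumed. Test age at first dose becomes 8 − 7 = 1 to 8 − 2 = 6 days. At last dose it becomes 19 − 7 = 12 to 19 − 2 = 17 days.

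**The case against.** The strongest reply is that this is a disclosed choice. Criterion 5 and section c.1) agree with each other, nothing is ambiguous, and no rule in the documents requires a test close to dosing. That stands: this is neither a contradiction nor an error.

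The second reply is that the benefit is tiny and its estimate stacks three outside assumptions. On those figures the likeliest result of retesting is that no pregnancy is found. That also stands, and it is why the point is optional. Frequent visits, a 12-day course and the lowest recommended dose narrow the gap further, although none of them detects an unrecognised pregnancy.

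Three stronger readings are tempting, and the documents do not support them:
- A reader might infer that fetal harm is being risked to a known degree. The documents give no fetal-risk data, so only exposure can be claimed.
- A reader might infer that contraception is neglected. The consent pages were removed and may cover it. The point concerns the test schedule only.
- A reader might infer that retesting must take place in both periods to protect the blind. It need not: a period 2 test given regardless of sequence reveals nothing about allocation.

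One could also argue that the interval is shorter than 28 days if screening falls inside the first baseline week. That is strained, because the remaining visits are scheduled after screening and two of them must still fit into that week.

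**Conclusion.** The point holds as an optional safety improvement with low expected yield. With one urine test at screening and self-report afterwards, a placebo-first woman begins levomilnacipran nominally about 28 days after day 1 of period 1, plus any screening gap. Nothing else in the supplied text closes that interval for an unrecognised pregnancy. The 28 days rests on a Monday-to-Friday quit week and on period 2 following period 1 directly, as the washout arrangement implies.

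The number of women and the expected conceptions rest on assumed proportions and serve only to show that the yield is well below one case. The case for change is that the test is already in use and the dispensing visit already exists. It has no bearing on sample size, alpha, power or the treatment comparison.

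**What to change.** Keep the screening test and self-report. In exclusion criterion 5 and the procedures (c.1 and c.2), add that all women of childbearing potential, whatever their sequence, repeat the urine pregnancy test at the second baseline-week visit of period 2, and that the initial supply is dispensed only if the test is negative. This closes the placebo-first gap. The sentence on identical procedures in c.2) would need a short exception if only period 2 is tested.

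The same test at the period 1 dispensing visit is a reasonable addition because no screening window is stated. It would also leave the two periods alike.

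Cost: one extra urine test per woman of childbearing potential, or at most two, at visits already scheduled. On the same assumptions, for completers, one test means 52 × 0.40 × 0.50 = 10.4 to 52 × 0.60 × 0.90 = 28.1, or about 10 to 28 tests in all; two means about 21 to 56. The visit total stays at 19. The downside is an occasional late exclusion. Very early pregnancy, and conception during the 12-day course, would remain uncovered.

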e) Outcome Measures: The primary outcome measure is the number of days of confirmed abstinence during the third week of each assessment period (out of a maximum of 5 days). A secondary outcome is the percentage of subjects who are abstinent at all five cessation visits.

Additionally at each visit, subjects will complete the Minnesota Nicotine Withdrawal Scale (MNWS), the Subjective State Scale (SSS) and the Questionnaire of Smoking Urges (QSU-Brief). Subjects will also be asked to report any adverse events they have experienced. The Minnesota Nicotine Withdrawal Scale, is a widely used scale to assess nicotine withdrawal symptoms.¹⁵ The positive affect and distress subscales of the SSS, have been found to be reliable at assessing these mood symptoms (alphas are 0.85 and 0.82, respectively).¹⁶ The Brief version of the Questionnaire of Smoking Urges (QSU-Brief) is a commonly used scale to assess nicotine craving with a score for each of two factors (i.e. intention and desire to smoke,

anticipation of relief from negative affect) calculated in order to examine several aspects of the urge to smoke.¹⁷

5 Potential Risks of Study Participation and Protection Against Risk

a. Risks to subjects: Levomilnacipran is generally well tolerated with the most common side effects reported being nausea / vomiting, constipation, excessive sweating, increased heart rate, urinary hesitation, palpitations and erectile dysfunction. Although occurring rarely other side effects including but not limited to mania, rash and allergic reaction, mydriasis, increases in blood pressure and abnormal bleeding have been occasionally reported. There is the possibility that when discontinuing levomilnacipran, subjects may experience a withdrawal syndrome that includes symptoms of dizziness, nausea and paresthesias. Questionnaires will be used to assess a variety of measures to ensure eligibility for the study and to measure outcomes of interest such as cigarette craving and withdrawal symptoms. Some of these questionnaires may ask questions that subjects would consider personal.

As with any medication, there is a risk that unanticipated side effects may occur.

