a.4) Data analysis: A paired t-test will be used to test treatment effect based on days of abstinence per quit assessment week (range 0-5, not necessarily consecutive) between levomilnacipran and placebo. Additional separate analyses for menthol and non-menthol cigarette smokers will be conducted. A two-sample t-test will be used to compare the difference in days of abstinence per quit assessment week for menthol cigarette smokers compared to non-menthol cigarette smokers.

Repeated measures Analysis of Variance (ANOVA) will be used for days of abstinence per quit assessment week, assuming mixed effects three-factor ANOVA model (“Order of phases” with two levels, “Treatment” with two levels, “Menthol cigarettes smoker” with two levels, subject effects are random); then use contrasts to compare treatment with placebo for all participants and for menthol cigarette smokers and non-menthol cigarette smokers separately. This approach allows us to investigate primary and secondary aims simultaneously, therefore, to potentially achieve higher statistical power. The use of paired t-tests, on the other hand, provides a proper tool for sample size determination as seen in the following section.

Generalized estimating equation (GEE) model will be used to analyze the longitudinal data, with the number of subjects able to maintain continuous abstinence on all 5 days throughout the quit week as the secondary outcome. Treatment effect (levomilnacipran vs. placebo) and cigarette type effect (menthol vs. non-menthol) will be estimated.

Secondary variables such as scores on the MNWS, SSS and QSU-Brief will be summarized by the mean, standard deviation, median and range. The change in these measures occurring between baseline (i.e. the first week of treatment) and the last day of the third week will be compared between drug and placebo. Similar two-factor ANOVAs will be used to analyze each of the calculated differences as the primary endpoint. Additionally, frequency of subject reported adverse events will be compared between treatments via the use of paired t-tests.

a.5) Power Consideration: The adequacy of planned sample sizes are assessed using two-sided paired t-test. We tested the “minimum detectable difference”, expressed as the number of standard deviations (i.e. “effect size”) for several sample sizes where the two-sided paired t-test is pre-set at a 5% significance level and 80% power. The variability is based on estimates found

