in the literature by others using these methods.⁵ With a total of 52 subjects completing the study (26 menthol smokers and 26 non-menthol smokers), we are able to detect an effect size of 0.57 standard deviations for the comparisons between levomilnacipran and placebo which is considerably smaller than the effect size of approximately 1.65 reported by Perkins et al for bupropion.⁵ Since we anticipate a 20% attrition rate, we are planning on enrolling 64 smokers in total (32 smokers of menthol cigarettes and 32 smokers of non-menthol cigarettes).

7 Data and Safety Monitoring Plan (DSMP)

The principal investigator in conjunction with the study physician will be responsible for monitoring adverse effects. At the conclusion of each visit subjects will be asked whether they have had any side effects. Any positive response will be followed up with questions regarding details of what the adverse effect was and the severity. To the extent possible, each adverse event will be evaluated to determine 1) its severity (mild, moderate, severe), 2) its relationship to the study medication; 3) its duration and 4) whether it constitutes a serious adverse event.

The participation of any subject will be discontinues if they develop a side effects of greater than moderate severity (as determined by the investigators) or develops any symptoms that in the opinion of the investigators would warrant discontinuation from the study. Participation in the study would also be discontinued if during the course of the study the subject develops a significant medical condition (regardless of whether it can be attributed to the study drug) or is initiated on medication that can be expected to interact with the measures being assessed or increase the risk of being on the study medication. The subject has the option of discontinuing their participation at any time for any reason. Adverse events will be reported to the IRB as required per IRB guidelines.

8 References

1. Fiore MC, et al. *Treating tobacco use and dependence: 2008 Update. Clinical Practice Guidelines. U.S. Department of Health and Human Services. Public Health Service*. Rockville, MD2008.
2. Hughes JR, et al. Antidepressants for smoking cessation. *Cochrane Database Syst Rev*. 2014;1:CD000031.
3. Perkins KA, et al. An efficient early phase 2 procedure to screen medications for efficacy in smoking cessation. *Psychopharmacology (Berl)*. 2014;231:1.

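### Subjects who choose to stay abstinent after the first quit week must leave, and the paired t-test then discards their observed first-period result

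*Combined protocol and SAP*

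**What the plan says.** Section 4 c) recruits smokers who "Indicate motivation to quit smoking". Section 4 c.2 describes the step between periods: "Since continued participation in the study will require subjects to resume smoking", subjects are told that they may stay abstinent if they wish, but "they would not be able to continue participation in the study if this were the case". The outcome is defined in Section 4 e): "The primary outcome measure is the number of days of confirmed abstinence during the third week of each assessment period", with a maximum of five.

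Section 6 a.4 lists two analyses of that outcome. The first: "A paired t-test will be used to test treatment effect based on days of abstinence per quit assessment week". The second: "Repeated measures Analysis of Variance (ANOVA) will be used for days of abstinence per quit assessment week, assuming mixed effects three-factor ANOVA model", with order, treatment and menthol status as factors and subject as a random effect. A GEE is planned for abstinence on all five days. Section 6 a.5 sizes the trial on 52 subjects who complete, 26 of each cigarette type, and enrols 64 to allow for 20% attrition.

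No section defines an analysis population, gives a missing-data rule, says which analysis is primary, or says whether the 20% includes exits due to continued abstinence.

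**The concern.** A subject who stays quit after period 1 has a complete period-1 value of the primary outcome, probably a high one, and no period-2 value. A paired difference does not exist for that subject, so the paired t-test drops a success that the trial has already measured. This differs from ordinary dropout because the reason for leaving is the outcome itself. If an effective drug makes quitters more likely to stay quit, more successes are lost after drug than after placebo, and the estimated effect moves toward zero.

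The direction matters because Section 1 says that a negative result would count against norepinephrine reuptake inhibition as a mechanism. The secondary outcome, the percentage abstinent at all five visits, is more exposed, because it counts the kind of week that is lost.

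**Working it through.** **1. The plan's own figure.** Section 6 a.5 sets its detectable difference for a test "where the two-sided paired t-test is pre-set at a 5% significance level and 80% power". The power of a paired t-test follows from a noncentral t with n − 1 degrees of freedom and noncentrality d√n.
- n = 26 pairs: detectable d = 0.572, and power at 0.57 is 79.8%. The stated 0.57 is thus the figure for one cigarette type.
- n = 52 pairs: detectable d = 0.396.
- Enrolment: 64 × 0.80 = 51.2, close to 52.

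All these counts are of complete pairs.

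**2. Who is lost, and from which analysis.**

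| Subject | Paired t-test | Mixed ANOVA, GEE |
|---|---|---|
| Five of five in period 1, resumes smoking, completes | used | used |
| Five of five in period 2 | used | used |
| Stays abstinent after period 1 and leaves | not used | period-1 week usable, plan silent |

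**3. Size of the bias.** The documents give no leaving rate, so this step rests on assumptions. Abstinent days are simulated as binomial out of 5 with a shared subject effect. Subjects with 5/5 in period 1 leave with probability q, which may differ by treatment. The completers' mean of (drug − placebo) is compared with the true difference.

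*Worked case.* True means are 2.34 and 1.72 days (difference 0.62), true 5/5 rates 15% and 8%, no period effect.
- Half of the 5/5 subjects leave: completers' difference 0.603; 0.603/0.620 − 1 = −3%.
- All leave (15.4% of drug-first and 8.1% of placebo-first subjects): 0.583; 0.583/0.620 − 1 = −6%. The 5/5 rates seen fall to 7% and 3%. By order, the difference splits into 0.38 (drug first) and 0.77 (placebo first), although no period or carryover effect was put in.
- A random-subject model that keeps the leavers' period-1 weeks gives 0.62.
- With no drug effect and equal leaving, the completers' difference stays at 0.

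*Range.* Placebo mean 2.1 days, gain 0.46 to 0.49, within-subject correlation 0.53 to 0.60.

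| Share of period-1 5/5 subjects leaving (drug vs placebo) | Completers' difference too small by |
|---|---|
| equal | 1% to 10% |
| 50% vs 25% | 5% to 9% |
| 100% vs 50% | 10% to 20% |

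At 50% leaving on both, completers' 5/5 rates fall from 19–21% to 14–15% on drug and from 12% to 8% on placebo. Other assumed gains (0.46 to 0.55) and correlations (0.55 to 0.69) gave +2% to −6% at equal leaving, 4% to 11% too small at 50% vs 25%, and 8% to 24% too small at 100% vs 50%. The pattern is stable, and the exact figures are not.

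**4. In days.** 5% of 0.46 is 0.02 day, and 20% of 0.49 is 0.10 day. In the worked case the SD of the paired difference is 1.72, so the standard error with 52 pairs is 1.72/√52 = 0.24 day.

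**5. Number of pairs.** If these exits come on top of the 20% attrition, a 10%, 20% or 30% loss leaves 51.2 × 0.9, 0.8 or 0.7, that is 46, 40 or 35 pairs (23, 20 or 17 per cigarette type). The per-type detectable effect rises to 0.61, 0.66 or 0.72 SD, and power at 0.57 falls to 74%, 68% or 60%. If the 20% already includes them, n is unchanged and only the selection remains.

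**The case against.** The case on the other side is strong on scope and size.

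- **Few may leave.** A reader might infer that the trial loses its most successful quitters as a group. The text does not support that. Only those who choose to stay quit after period 1 leave, and everyone who succeeds in period 2 is kept. At the rates in Section 4 d), leaving forfeits up to 9 × $20 + 5 × $15 + $60 = $315, and recruitment notices say that this is not a treatment study. This stands.
- **Not only top scores.** Section 4 c.2 sets no five-of-five condition. Someone with three or four abstinent days who is abstinent at the end may also leave. The simulations simplify here.
- **The plan may already cope.** The mixed ANOVA and the GEE can use one-period subjects, and a.4 itself presents the paired t-test as the tool for sample size. The 52 completers are a power assumption, not an analysis set. So a completers-only rule cannot be read into the plan. But neither can its opposite: repeated-measures ANOVA is often run on complete cases, and an ordinary GEE assumes that missingness is unrelated to outcome, which is not so here.
- **The bias is small beside the noise.** At 0.02 to 0.10 day it is well under one standard error. The upper part of the range needs drug quitters to leave at twice the placebo rate. No section supports that rate, and medication stops when the quit week ends. This stands too.
- **Recovery by the mixed model is partly built in.** In the simulations leaving depends only on treatment and the observed period-1 score, which is the condition that a likelihood analysis needs. If leaving also depends on unmeasured motivation, the recovery is untested.

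**Conclusion.** The concern holds in a limited form. The exit rule is explicit, and the paired t-test cannot use those who leave under it, so some observed successes are discarded for an outcome-related reason. What the ANOVA and GEE would do with them is undefined.

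The mechanism is certain; the size is not. Under assumed rates the primary difference is pulled toward zero by about 0% to 10% at equal leaving and about 5% to 20% at a two-to-one ratio. The completers' five-of-five percentages are understated even at equal leaving. A reader might infer that a large underestimate, or a false positive, is built in. The documents give no leaving rate to support the first. As to the second, the paired difference stayed at zero with no drug effect and equal leaving.

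The change is worth making because the better analysis is already in the plan and only has to be specified.

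**What to change.** In Section 6 a.4:

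1. Name the random-subject mixed model as the primary analysis, with treatment and period terms. Order as a main effect alone does not adjust for period, so state the period term. Fit the model by likelihood to every randomised subject with at least one quit week, including those who leave after period 1 because they remain abstinent.
2. Keep the paired t-test as a completers sensitivity analysis.
3. Analyse the five-of-five outcome with a subject-level model using all observed quit weeks and a period term, supported by a comparison of period 1 alone. Do not rely on raw percentages per condition. When leaving is unequal they favour the drug, because drug-first leavers count in the drug rate but are missing from the placebo rate: about 1 point with no drug effect at 100% vs 50% leaving.
4. Record leaving because still abstinent as a separate reason, and report it by period-1 treatment. In a.5, say whether the 20% attrition includes it.

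The exit rule itself is not touched. The cost is wording and one data field, with no extra visits or subjects. The downside is that the primary estimate relies on a model and assumes that leaving depends on observed data.
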